#### 10.8 Annual progress report

The sponsor/investigator will submit a summary of the progress of the trial to the accredited METC once a year. Information will be provided on the date of inclusion of the first subject, numbers of subjects included and numbers of subjects that have completed the trial, serious adverse events/ serious adverse reactions, other problems, and amendments.

#### 10.9 Temporary halt and (prematurely) end of study report

The sponsor will notify the accredited METC and the competent authority of the end of the study within a period of 90 days. The end of the study is defined as the last patient's last visit.

The sponsor will notify the METC immediately of a temporary halt of the study, including the reason of such an action.

In case the study is ended prematurely, the sponsor will notify the accredited METC and the competent authority within 15 days, including the reasons for the premature termination.

Within one year after the end of the study, the investigator/sponsor will submit a final study report with the results of the study, including any publications/abstracts of the study, to the accredited METC and the Competent Authority.

#### 11. STRUCTURED RISK ANALYSIS

#### 11.1 Potential issues of concern

#### a. Level of knowledge about mechanism of action

Recently it was shown that the mTOR inhibitor sirolimus can cause tumour cells to undergo growth arrest and differentiation in APC-deficient mice (14). Signalling through the mTOR pathway is necessary for epithelial cell proliferation and tumour growth (15, 16). It was shown that mTOR complex 1 (mTORC1) activity is required for the proliferation of APC-deficient enterocytes. This complex mediates inhibition of eEF2 kinase, which is needed for the proliferation of APC-deficient cells. Sirolimus targets eEF2 resulting in growth arrest and differentiation of tumour cells. The effect of sirolimus on colonic adenoma regression was confirmed in other mice studies, with one of them showing beneficial effects in the small bowel (17-22). Sirolimus seems to inhibit polyp formation and could even lead to regression of polyps (21, 23). Moreover, it seems to increase survival and time to progression to dysplasia (20, 21).

# b. Previous exposure of human beings with the test product(s) and/or products with a similar biological mechanism

As previous described, sirolimus is a registered drug for patients who have undergone a renal transplantation. Details about the exposure of human beings with sirolimus are clearly described in the SPC text. Sirolimus has never been investigated in patients with FAP. However, since February 2014 an American center has been recruiting 15 participants for a pilot study aiming to investigate if mTor pathway activation decreases in patients with surgically-resectable desmoid tumors that are removed following pre-operative treatment with sirolimus. That study is being conducted in children and young adults (up to 29 years), which includes patients with FAP. Results are expected in 2016 (25).

# c. Can the primary or secondary mechanism be induced in animals and/or in *ex-vivo* human cell material?

As far as we know, sirolimus has never been investigated in ex-vivo human cell material of FAP patients. However, as written in chapter 12.1a the primary outcome and some of the secondary outcomes were found effective in mouse models.

## d. Selectivity of the mechanism to target tissue in animals and/or human beings

Version number: ,date 35 of 40

See the SPC text and chapter 12.1a for explanations of working mechanisms. Known side-effects can be found in chapter 6.2 and all other drugs that could interact with sirolimus can be found in Table 1.

## e. Analysis of potential effect

See chapter 6.2 for side-effects of sirolimus. The incidence of side-effects increases at a rising trough level of sirolimus. The dosing regimen as nationally recommended for patients with a renal transplantation reaches blood level concentrations sufficient to achieve a clinical result. As our proposed dosing regimen is similar to that but on the lower side, we believe effect on the intestinal mucosa can be expected with a limited risk of side-effects. No data from human studies is available on the required level of sirolimus in full blood to achieve intestinal effects. See chapter 6.4 for further risks and benefits.

## f. Pharmacokinetic considerations

See the SPC text for pharmacokinetics of sirolimus.

#### g. Study population

The study population consists of patients with FAP, which is a potentially life threatening disease. The patients that will be included are likely to undergo a subtotal colectomy with ileoanal pouch anastomosis or an end ileostomy on a short term due to the severe degree of polyposis. These invasive types of surgery are accompanied with a significant risk of comorbidities (29). Even after surgery, patients will develop polyps in the remaining intestinal tissue and therefore surveillance sigmoidoscopies are needed to prevent the development of cancer (5, 30-32). There is currently no alternative treatment available for these patients. Therefore, a medical treatment to postpone or even prevent surgery could be beneficial. If a polyp reducing effect is shown in the intestinal tissue, this therapy could possibly also be beneficial in postponing a preventive colectomy in patients with FAP who have their colon in situ and in postponing a duodenectomy in patients with severe duodenal polyposis.

#### h. Interaction with other products

See the SPC text for interactions of sirolimus with other products. To avoid these interactions, the use of any of these products is not allowed when enrolling in this study (see exclusion criteria). If any of these products are started during the study, additional trough level testing will be done or patients will be withdrawn from this study (depending on the expected interaction).

Version number: ,date 36 of 40

### i. Predictability of effect

The combination of endoscopic measurements and laboratory measurements will provide relevant data, both clinical and translational, that will help answering the research question. If no effects on polyp size are seen, laboratory measurements will provide us with useful translational information. If, for example, an effect is seen in cell proliferation or mTOR targets and the chosen dosing regimen is safe, a future study could evaluate the effect of a higher dose for a longer period of time.

#### j. Can effects be managed?

A renal transplantation physician, working at the AMC, is actively involved in this study. She is experienced in treating patients with sirolimus and therefore she will assist us if needed. Patients will be given contact details of the investigating team and in case of emergencies when the investigating team cannot be contacted, the patient can contact the gastroenterologist that is on call.

#### 11.2 Synthesis

To reduce the risk of side-effects related to sirolimus, a relatively low trough level will be managed. Furthermore, regular telephonic contact, trough level testing, laboratory testing and physical examination will lead to an early detection of any side-effects. We believe this could help patients, who would otherwise need surgery on a short term. As of today no strict contraindications exist for the use sirolimus. However, we exclude patients using medications that could interact with sirolimus. Furthermore, patients with specific laboratory abnormalities as well as patients with specific conditions (such as a deep venous thrombosis or sucrose insufficiency) that could deteriorate due to the use of sirolimus or that could influence the effect of sirolimus are excluded.

We will use tattoos with SPOT™ for marking the polyp sites, which has been used for many years in colonoscopy practice (26). No side-effects of SPOT have been described in the literature. Furthermore, colonic biopsies are accompanied by a minimal risk of perforation, bleeding and infection. These complications have been described in some case reports after hot biopsy but mostly in patients with pre-existent ulcerative colitis or infectious colitis. Bleeding after hot biopsy has been reported to occur in up to 0.26% and perforation in up to 0.01% after hot biopsy. During our study only cold biopsies will be obtained. Only case reports have reported on complications after cold biopsy (27, 28). These complications are cited in the written patient information.

Version number: ,date 37 of 40

In our opinion, treatment with sirolimus could help patients, who would otherwise need surgery on a short term base associated with a significant risk of morbidity and mortality. By applying the above risk management, we believe this treatment is justified. Results of this pilot study could help in creating a future trial assessing the effect of sirolimus in patients with FAP.

Version number: ,date 38 of 40

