#### **Baseline**

- · Medical history & physical examination (including vital signs)
- · Laboratory tests (hematology¹, chemistry², pregnancy test, urine specimen)
- · HRQoL questionnaires
- · LGI endoscopy
- · Day 7: Trough level testing of sirolimus on day 7 after start study drug and weekly until the therapeutic range has been achieved

#### Month 1 & 2

· Monthly telephone check-ups to assess the occurrence of (non-)serious adverse events

## Month 3

- · Monthly telephone check-ups to assess the occurrence of (non-)serious adverse events
- · Medical history & physical examination (including vital signs)
- · Laboratory tests (hematology, chemistry, pregnancy test, urine specimen)
- · HRQoL questionnaires
- $\cdot \textit{Trough level testing of sirolimus and weekly until the the rapeutic range has been achieved} \\$

## Month 4 & 5

· Monthly telephone check-ups to assess the occurrence of (non-)serious adverse events

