#### Lab results:

- -Abnormal laboratory results (assessed within 14 days prior to start of study drug):
  - -Significant abnormalities in hepatic function

-ALAT, ASAT, GGT, AF, LDH: > 1.5 times ULN

-Significant hematologic abnormalities

-Hb: <7.0 mmol/L

-Thrombocytes: <100 10E9/L

-Leukocytes: <4.0 10E9/L

-Increased fasting serum cholesterol or triglyceride (whether or not on lipid-lowering therapy)

-Serum cholesterol: >7.8 mmol/L

-Serum triglycerides: >4.5 mmol/L

-Increased glucose (venous, fasting): >6.4 mmol/L

-Electrolyte abnormalities

-Total serum calcium (corrected for albumin): <2.0 mmol/L

-Potassium: <3.0 mmol/L

-Phosphate: <1.3 mmol/L

-Calculated glomerular filtration rate (GFR) less than 40 mL/min/1.73m2 using the simplified Modification of Diet in Renal Disease (MDRD) formula

-Urine specimen:

-Spot urine protein to creatinine ratio (UPr/Cr) greater than or equal to 0.5

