#### 5.2 Use of co-intervention

Female participants who are sexually active must use adequate contraception as confirmed by three monthly pregnancy tests and male patients need to use adequate contraception as well. Adequate contraception needs to be continued until 12 weeks after therapy. Furthermore, any new concurrent medication that is started during the study needs to be reported. If known to have an interaction with sirolimus, an additional trough level measurement needs to be done. Patients will visit the AMC at baseline, month 3 and month 6 for the interventions as mentioned in chapter 1 'Study design' (physical examinations, laboratory tests, pregnancy test, urine specimen , questionnaires) and weekly for sirolimus trough level testing until the target range has been achieved. Moreover, monthly telephone check-ups will be performed.

Endoscopies that take place at baseline and at 6 months follow-up are not considered cointerventions, as these are performed in a frequency that is consistent with our practice guidelines. Tattoos that are placed during these procedures are considered additional interventions and biopsies that are done can partly be considered as additional interventions, as some of these would have been done in routine care: 5 biopsies of normal mucosa are additional, 5 biopsies of adenomatous tissue are part of routine care.

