As described in chapter 6.2, a significant polyp reducing effect of sirolimus is to be expected. The patients that will be included, are likely to undergo a subtotal colectomy with ileoanal pouch anastomosis or an end ileostomy on a short term base due to the severity of polyposis. These invasive types of surgery are accompanied with a significant risk of comorbidities (29). Even after surgery, patients will develop polyps in the remaining intestinal tissue and therefore surveillance sigmoidoscopies are needed to prevent the development of cancer (5, 30-32). There is currently no alternative treatment available for these patients. Therefore, a medical treatment to postpone or even prevent surgery could be beneficial. If a polyp reducing effect is shown, this therapy could possibly also be beneficial in postponing a preventive colectomy in patients with FAP who have their colon in situ and in postponing a duodenectomy in patients with severe duodenal polyposis.

Version number: ,date 18 of 40

Table 1. Side-effects of sirolimus (SPC)

System/organ	Very frequent	Frequent	Less frequent	Seldom
	(≥1/10)	(≥1/100 to <1/10)	(≥1/1000 to <1/100)	(≥1/10.000 to <
Infections	Pneumonia Fungal infection Viral infection Bacterial infection Herpes simplex infection Urinary tract infection	Sepsis Pyelonephritis CMV infection Herpes zoster infection	Clostridium difficile colitis Mycobacterial infection (incuding tuberculosis) EBV viral infection	
Neoplasms, benign, malignant and non-specified (including cysts and polyps)		Skin cancer	Lymphoma/ post- transplantation lymphoproliferative conditions	
Blood and lymphatic disorders	Thrombocytopenia Anemia Leukopenia	Hemolytic-uremic syndrome Neutropenia	Pancytopenia Thrombotic thrombocytopenic purpura	
Hepatic and biliary disorders			Hepatic failure	
Immune system disorders		Hypersensitivity disorders such as anaphylactic/anaphylactoid reactions, angio-edema		
Feeding and metabolic disorders	Hypokalemia Hypophosphatemia Hyperlipidemia (such as Hypercholesterolemia) Hyperglycemia Hypertriglyceridemia Diabetes mellitus			
Nervous system disorders*	Headache			
Cardiac disorders	Tachycardia	Pericard effusion		
Vascular disorders	Lymphocele Hypertension	Venous thrombosis (such as deep venous thrombosis)	Lymphedema	
Respiratory, chest and mediastinal disorders		Pulmonary embolism Pneumonitis Pleural effusion Epistaxis	Pulmonary hemorrhage	Alveolar protein

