#### 7. METHODS

## 7.1 Study parameters/endpoints

#### 7.1.1. Main study parameter/endpoint

- Size of 5 marked polyps in 5 patients with FAP and a large intestinal polyp burden
- Safety outcomes reported by summary analysis of adverse events, clinical laboratory abnormalities and regular physical examination

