#### 7.2 Study procedures

## Baseline and follow-up measurements and monitoring

- -Medical history and physical examination (including vital signs) at baseline and at three monthly visits
- -Lab testing at baseline and at three monthly visits: pregnancy test, urine specimen, hemoglobin, thrombocytes, cholesterol, triglycerides, glucose, potassium, phosphate, calcium, LDH, ALAT, ASAT, GGT, AF, leukocytes, creatinine, albumin.
- -Three monthly HRQoL questionnaires
- -Trough level testing of sirolimus (using the LC-MS/MS method) on day 7 after start study drug and weekly until the therapeutic range has been achieved, after which the next trough level will be measured at three months
- -Monthly telephone check-ups to assess the occurrence of (non-)serious adverse events

Version number: ,date 22 of 40

-LGI endoscopies at baseline and at six months. Endoscopic procedures will be performed after bowel preparation with sedation according to the standard of care by experienced endoscopists.

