#### 7.3.1 Specific criteria for withdrawal

Participants will be withdrawn from treatment under the following circumstances:
-If any of the exclusion criteria apply during the study

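### The first on-treatment safety panel is at month 3, although blood is already drawn from day 7 for the trough level; those draws could carry the panel at little cost

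*Combined protocol and SAP*

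**What the plan says.** Section 7.1.1 lists, as a main parameter beside polyp size, "Safety outcomes reported by summary analysis of adverse events, clinical laboratory abnormalities and regular physical examination". Section 11.2 builds its risk argument on the claim that "regular telephonic contact, trough level testing, laboratory testing and physical examination will lead to an early detection of any side-effects", and section 8.5 also names regular laboratory testing as a means of safety monitoring.

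The schedule is in sections 3, 5.2 and 7.2. Section 7.2 specifies "Lab testing at baseline and at three monthly visits", and section 5.2 makes clear that these visits are at baseline, month 3 and month 6. In between, patients attend "weekly for sirolimus trough level testing until the target range has been achieved". Section 3 gives the day-7 visit as a trough measurement only, and months 1 and 2 as telephone contacts. Under section 5.1, a patient whose level is in range has no further draw until month 3. The month-3 entry in section 3 again provides for "Trough level testing of sirolimus and weekly until the" level is in range.

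Section 7.3.1 withdraws a patient from treatment "If any of the exclusion criteria apply during the study". The exclusion criteria in 4.3 include numeric laboratory limits, introduced as "Abnormal laboratory results (assessed within 14 days prior to start of study drug".

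**The concern.** An endpoint can contain only what the schedule measures. Many of the effects that Table 1 (section 6.4) puts in its most frequent class, such as "Thrombocytopenia Anemia Leukopenia" and the lipid, glucose and electrolyte changes, are laboratory findings that a telephone call may not bring out. That last step is a judgement; the protocol does not say it.

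With no panel before month 3, an abnormality that arises and resolves in the first half of treatment does not enter the primary safety summary. One that persists is found at month 3, but its time of onset is unknown and nobody could act on it sooner. The month-6 panel coincides with the end of treatment, so each patient has one scheduled panel that can influence continued dosing.

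Dose adjustment is a natural time to look, because sections 6.4 and 11.1e link side-effects to rising trough levels. Patients are being bled at exactly that time, for another purpose.

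**Working it through.** The plan has no sample size, power or alpha figure to reproduce (section 4.4; section 9 is descriptive). The check is a count of the schedule.

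**Inputs**
- Five patients (4.4) and six months of treatment (3).
- Panels at baseline, month 3 and month 6 (3, 5.2, 7.2). The phrase in 7.2 could be read as three visits a month apart; section 5.2 rules that out.
- Trough draws at day 7, then every 7 days until in range (5.1).
- Month = 365.25/12 days, so month 3 = day 91.3 and month 6 = day 182.6.

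**Current schedule**
- Panels after baseline: 2 per patient, 5 × 2 = 10 in the trial.
- Panels after baseline and before month 3: 0.
- Share of treatment elapsed at the first on-treatment panel: 91.3/182.6 = 0.50.
- Blood draws in that window: at least one per patient (day 7), plus one per dose adjustment.

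**With the panel added to trough draws**

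Let k be the number of weekly draws after day 7. The plan does not give k, so 0 to 4 is an assumed range. Panels before month 3 = 1 + k; last such panel on day 7 + 7k; remaining gap = 91.3 − (7 + 7k).

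| k | Panels before month 3 | Last on day | Days left without a panel |
|---|---|---|---|
| 0 | 1 | 7 | 84 |
| 1 | 2 | 14 | 77 |
| 2 | 3 | 21 | 70 |
| 3 | 4 | 28 | 63 |
| 4 | 5 | 35 | 56 |

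Extra panels before month 3: 5 × 1 = 5 if every patient is in range at day 7, and 5 × 5 = 25 if every patient needs four further draws. The guaranteed minimum raises the trial total from 10 to 15.

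**What closing the gap would take**

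Take month 1 as day 30 and month 2 as day 61. Day 7 plus month 2 leaves a longest gap of 61 − 7 = 54 days. Day 7 plus months 1 and 2 leaves the largest of 30 − 7 = 23, 61 − 30 = 31 and 91 − 61 = 30, that is 31 days. Months 1 and 2 are telephone contacts now, so these panels need new visits.

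**Overlap with the plan's own limits**

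Table 1 lists 36 entries in its most frequent class. Thirteen are laboratory findings: 3 blood, 6 metabolic, 1 proteinuria, 3 laboratory tests. Twelve of these have their own limit in 4.3 (creatinine through GFR); diabetes mellitus is covered only through glucose. Eleven of the twelve can be read from blood; proteinuria needs urine.

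**Size of the downside**

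One withdrawal is 1 of 5 patients and 5 of 25 marked polyps. Section 7.4 allows no replacement, and 7.5 requires a follow-up endoscopy only after at least one month on drug.

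**The case against.** The strongest reply is that nothing in the plan is broken. The three-monthly schedule is consistent throughout, and the documents set no panel frequency that it breaches. Product information is given by reference to the SPC, so whether three-monthly panels are too sparse here cannot be judged from these documents. The plan controls risk mainly through exposure: a 5–8 ng/ml target, a 2 mg start, no other immunosuppressants, and a tablet supply of about 2000/(5 × 182) = 2.2 mg per patient per day. Section 11.2 credits early detection to four means together, and two of them, calls and trough levels, operate before month 3. Section 8.4 allows extra tests for a known event. All of this stands, and it is why the point is an improvement and not an error.

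A second reply is that the remedy barely touches the gap: 91 days becomes 84 for a patient in range at day 7. That also stands. The benefit is larger only in patients whose dose is being adjusted.

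A third reply is that more panels give more chances to cross an entry limit, for example phosphate below 1.3 mmol/L when hypophosphataemia is in the most frequent class, and so to lose a patient's polyp outcome. This is a real cost. A confirmation rule limits it but does not remove it.

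Two stronger readings are tempting. A reader might infer that some stated share of abnormalities would be missed. The documents give no onset or duration, and Table 1 comes from transplant patients mostly on combined immunosuppression, so no detection percentage is supported. A reader might also infer that the 4.3 laboratory limits are settled on-treatment stopping limits. They carry a 14-day pre-start window; their use during treatment rests on the literal wording of 7.3.1.

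**Conclusion.** The point holds as a low-cost improvement. Laboratory abnormalities belong to a main endpoint, section 11.2 relies on laboratory testing for early detection, and no panel is scheduled until about halfway through treatment, although every patient has blood drawn at day 7. The schedule count needs no assumption beyond calendar months.

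The guaranteed gain is one early on-treatment value per patient and a cut in the longest gap before month 3 from about 91 to 84 days. Anything beyond that depends on how many dose adjustments occur, which is unknown. Months 3 to 6 have an equal 91-day interval, with draws in between only if the month-3 level is out of range.

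It does not follow that monitoring is unsafe, that section 11.2 is untrue as a whole, or that the proposed panels would close the gap. Entry limits, monthly questioning and the involvement of a transplant physician reduce the risk, though 4.3 still admits liver tests up to 1.5 times ULN and a GFR down to 40. None of these measures supplies an on-treatment panel.

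**What to change.** - In sections 3, 5.1 and 7.2, run the existing haematology and chemistry panel on the day-7 draw for all five patients, and on each further weekly trough draw while the dose is being adjusted, including after month 3. Draw it fasting, because the 4.3 lipid and glucose limits are fasting limits.
- Report laboratory results by visit. Day 7, month 3 and month 6 form the common set; list adjustment-phase panels separately, with the number of panels per patient.
- State in 7.3.1 whether the 4.3 laboratory limits apply on treatment. If they do, require confirmation on a repeat before withdrawal (within 7 days is one option), with the safety committee free to stop treatment at once.
- Limit the early-detection sentence in 11.2 to what the schedule supports.

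**Cost.** Protocol wording, at least five extra panels, and fasting at those visits. No new routine visit or venepuncture is needed; a confirmatory repeat may need one for a patient already in range. An earlier withdrawal is possible, and in the first month it could leave that patient without a polyp outcome.

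A panel at months 1–2, which would largely close the remaining gap, needs new visits and is a separate clinical decision.
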